## **10.2 Immunologic Response**

Peripheral blood samples and urine specimens will be obtained at time points according to the Schedule of Events. All samples will be shipped to and processed by one or more central laboratories.

Seventy (70) mL heparinized blood and 10 mL of non-heparinized blood will be drawn at each time point and used for analysis as outlined below. Peripheral blood mononuclear cells (PBMCs) will be isolated from heparinized blood samples by Ficoll separation. Isolated PBMCs will be utilized for immunophenotyping analysis using flow cytometry, DNA isolation and subsequent T cell receptor sequencing, intracellular cytokine analysis, and ELISPOT assays as described below. Serum will be collected from non-heparinized blood samples and stored for batch analysis of antibody titers and serum cytokines/chemokines.

Twenty-four (24) mL of urine will be collected at each time point. Part of each sample will be centrifuged and cell counts determined. If there are sufficient numbers of cells, samples may be analyzed by multicolor flow cytometry using standard procedures to examine lymphocyte subsets. The remainder of each sample will be frozen for batch analysis of inflammatory cytokines.

In addition to the analyses specified below, subsequent exploratory mechanistic analyses, the nature of which will be determined by emerging PBMC and tumor biopsy data on the immunological environment pre- and post-vaccine, may also be performed.

### **10.2.1 Production of Interferon-gamma from CD8+ T Cells (ICS Assay)**

The immune response will be evaluated by antigen-specific flow cytometry and/or ELISPOT analysis for IFN $\gamma$  production by patient T cells. These ICS assays will be done under Good Laboratory Practice (GLP)-like conditions using standard operating procedures and validating assays with standardized negative and positive controls. Processing of all patient samples by a single facility in large batches will be performed to minimize assay variability between samples.

Thawed and isolated PBMCs will be challenged or restimulated with specific tumor vaccine antigens as follows:

- PBMCs alone (negative control)
- PBMCs + PMA + Ionomycin (positive control)
- PBMCs + vesigenurtacel-L whole cell lysates (vaccine)
- PBMC + a cocktail of known shared antigens, including survivin, LAGE-1s, MAGE-A1, and MAGE-A3

A maximum of four stimulation conditions at each time point per blood sample will be set up.

For the flow cytometry assay, following in vitro stimulation, cells will be harvested and labeled with antibodies to cell surface markers, including CD4 and CD8, and then fixed, permeabilized, and stained for the indicated intracellular markers, including IFN $\gamma$  and grzB. Samples will be analyzed by flow cytometry immediately after staining.

For the ELISPOT assay, the frozen PBMCs will be thawed, antigen challenged, plated for analysis of IFN $\gamma$  and grzB production by ELISPOT assay, and analyzed in triplicate for each time point for each patient. If cells are limiting, IFN $\gamma$  analysis will be prioritized. Following incubation, samples will be quantitated in an automated ELISPOT reader.

The frequency of IFN $\gamma$  producing CD8+ cells is thought to mirror the frequency of cytotoxic CD8+ cells. However, cytotoxicity is primarily mediated by perforin and granzymes following granule exocytosis. In some instances IFN $\gamma$  secretion and granule exocytosis are uncoupled. Therefore, the direct measurement of grzB secretion by ICS may provide a more direct readout for antigen-specific granule exocytosis and cytotoxicity. For clinical efficiency it may be important to detect both IFN $\gamma$  secretion and grzB exocytosis. Antigen specificity of the ICS response will be evaluable by comparing responses generated using the various stimulator cell populations and specific shared bladder cancer antigens as indicated. This will also enable separation of the ‘allo-antigen’ specific response with the potential parent cell line tumor-antigen-specific response. Positive responses will be defined as a greater than two-fold increase in the number of IFN $\gamma$  positive CD8+ T cells compared to baseline.

### **10.2.2 PBMC Counts**

Total PBMC counts will be obtained from each patient from two sources. First, blood hematology will be performed for each patient at Baseline and the treatment weeks indicated in the Schedule of Events at the clinical centers. Second, the peripheral blood phenotyping analysis (described below) will be performed quantitatively for each of the markers indicated, providing a secondary measure of PBMC subsets defined by expression of the individual markers indicated.

Total PBMC counts may be utilized as a surrogate endpoint for the overall health of a patient’s immune system.

### **10.2.3 Phenotyping of Blood Lymphocyte Subsets**

Following alkaline lysis of red blood cells using standard procedures, peripheral blood samples will be stained using antibodies specific for the following cell markers: CD3, CD4, CD8, CD19, CD25, CD45, CD56, and FoxP3. Samples will be analyzed by multicolor flow cytometry using standard procedures.

Flow cytometric analysis of patient peripheral blood samples will quantitatively determine the frequency and number of lymphocytes (CD45+), B cells (CD45+CD3+CD19+), helper T cells (CD45+CD3+CD4+), cytotoxic T cells (CD45+CD3+CD8+), regulatory T cells (CD3+CD4+CD25+FoxP3+), and natural killer cells (CD45+CD56+) at baseline and over the course of therapy. In addition a T cell activation panel (CD4, CD8, Ki67, perforin, IFN $\gamma$ ) will be performed before and after in vitro stimulation with PMA/ionomycin, a regulatory T cell panel (CD4, CD25, FoxP3, CD127, CD45-RA), a myeloid suppressor cell panel (CD39, CD11b, CD124, CD45, HLA-DR, CXCR4), and T cell suppression panel (CD4, CD8, CTLA-4, PD-1, Tim-3) will be performed on freshly isolated PBMC.

#### **10.2.4 TCR Sequencing**

ELISPOT and intracellular cytokine assays are frequently used to monitor patient immune response to immunotherapy, despite the knowledge that these assays have not previously been strongly predictive of clinical response. Thus, prognostic immune monitoring assays are highly desired. If T cell receptor (TCR) clones are present that recognize antigens introduced by vesigenurtacel-L, clonal expansion of these cells is indicative of effective vaccination and potentially predictive for the presence of patient-tumor antigen specific T cells.

TCR genomic DNA extracted from tumor tissue and PBMCs will be amplified and sequenced.

The Phase 2 study is designed to explore the feasibility of application of this approach to later phase studies. In addition, data generated using this approach during Phase 2 may later be compiled with a larger data set to investigate the prognostic significance of individual TCR sequences before and during treatment with vesigenurtacel-L.

Although this assay is potentially predictive of a clinical response, it remains an exploratory endpoint in this trial because this analysis can only be confirmed once expansion of individual T cell clones is found to correlate (or not) with improved patient survival. Thus, the TCR sequencing data will be analyzed both before the survival data has matured in order to ascertain whether there are conserved sequences expanded for patients with similar HLA types but also to determine whether a clonal TCR signature emerges that has the potential to be used as a predictive biomarker for response in subsequent trials.

#### **10.2.5 Analysis of Infiltrating T Cells (Post-Treatment Tumor Biopsy)**

If a biopsy is performed at any time post-treatment, the tissue will also be examined for presence of infiltrating T-cells (TILs). Two-color fluorescence immunohistochemistry (IHC) and multicolor fluorescence-activated cell sorting analysis will be used for quantification of CD8+ T cells and measurement of their activation status (CD69-expression) and cytotoxic activity (CD107a-expression) *in situ*. These data will be correlated with clinical response.

#### **10.2.6 Antigen Screening of Resected Tumor Tissue**

A sample containing at least 4, non-stained, 10 micron sections will be collected for the purpose of screening the tissue for representative antigen expression (LAGE-1, NY-ESO-1, MAGE-[A1-10], CT7, CT10, GAGE, etc.), expression of MHC class I, and expression of immunosuppressive molecules, including, for example, CTLA-4, PD-L1 and PD-1, by mRNA expression and/or IHC analysis. If slides are not available, FFPE tissue ( $\geq 50$  microns) is also acceptable. These data will be retrospectively correlated with immune response to determine if a particular antigen expression profile may predict response to treatment.

The tumor arrays will be processed by IHC and PCR according to standard methods. Bound antibodies will be visualized by using the avidin-biotin complex method according to the recommendations of the supplier (Vectastatin Elite ABC Kit; Vector Laboratories Inc., Burlingame, CA). Diaminobenzidine will be used as chromogen. 57B staining will be classified as follows: no staining; “weak,” indicating low-intensity staining regardless of positive cell percentages or medium intensity staining of no more than 20% of cells; “moderate,” indicating medium-intensity staining of more than 20% of cells or high-intensity staining of no more than 20% of cells; “strong,” indicating high-intensity staining of more than 20% of cells. Only

moderately and strongly positive cases will be considered positive. For PCR based analysis, total RNA will be isolated from collected tissue samples and reverse transcribed to cDNA using standard methods. The expression of tumor antigens from cDNA samples will then be interrogated using real-time PCR and a variety of specific tumor antigen probes.

## 11.0 SAFETY ASSESSMENTS

Safety will be assessed throughout the study by a qualified physician, physician assistant, or nursing staff. Measurements used to evaluate safety will include history, physical examination, vital signs, clinical laboratory tests, urinalysis, 12-lead ECG, and monitoring for AEs. AEs will be graded according to the National Cancer Institute Common Terminology Criteria for Adverse Events Version 4 (NCI-CTCAE v4.03) [NCI, 2010].

Laboratory measurements that deviate significantly (as determined by the investigator) from previous measurements may be repeated. If warranted, additional or more frequent testing than is specified in the protocol should be done to provide adequate documentation of AEs and the resolution of AEs.

### 11.1 Physical Examination

Medical and physical examinations must be performed by a qualified physician, nurse practitioner, or physician assistant and should include a thorough review of all body systems at Screening, Baseline, and End of Treatment. Examinations should be performed as listed on the schedule of events. Physical examinations will include vital signs (heart rate, temperature, respiratory rate, and blood pressure). Blood pressure, heart rate, and respiration rate will be measured after resting in a semi-supine or supine position, and patients must be in the same position at each assessment for at least 5 minutes before and during the assessment. Physical examinations at Weeks 7 and 14 in Phase 1 and Week 13 in Phase 2 are limited to vital signs and symptoms.

### 11.2 Clinical Laboratory Tests

Patients will have blood samples collected for routine clinical laboratory testing. The clinical laboratory parameters will be analyzed at the site's local laboratory. Laboratory assessments to be completed will include hematology, chemistry, and urine or serum pregnancy test (females of childbearing potential).

Laboratory assessments will be defined as follows:

- **Chemistry:** To include sodium, calcium, total protein, albumin, creatinine, blood urea nitrogen, total bilirubin, alkaline phosphatase, AST, ALT, potassium, chloride, bicarbonate, lactate dehydrogenase, and glucose.
- **Hematology:** To include white blood cell (WBC) with differential, platelet count, hemoglobin, and red blood cell (RBC) count.
- **Urine or serum pregnancy test** – See section 11.7 below for further details.

Additional laboratory assessments may be conducted throughout the study as medically necessary.

### **11.3 Urinalysis**

Patients will have urine samples collected for routine urinalysis. The urinalysis will include color, appearance, and dipstick for specific gravity, protein, white blood cell-esterase, glucose, ketones, urobilinogen, nitrite, WBC, RBC, and pH. Microscopic analysis of urine will be performed if indicated based on macroscopic examination and urine dipstick results.

### **11.4 ECG**

The following parameters from 12-lead electrocardiograms (ECG) will be evaluated: heart rate, PR interval, QRS duration, QT interval, and QTcF interval.

### **11.5 Autoimmune Monitoring**

Autoimmune monitoring will occur through laboratory measurements of ANA, TSH, erythrocyte sedimentation rate (ESR), and C-reactive protein. Other tests, such as rheumatoid factor (RF), T3, T4, and thyroid antibodies may be performed as clinically indicated. Furthermore, periodic physical examinations, including eye exam for dry eyes, lymph node and joint assessment, and skin exam for vitiligo and rashes, will be performed.

### **11.6 Injection Site Reactions**

The grading scale for injection site reactions (ISRs) used in this trial can be found in Appendix 3. Grade 1 ISRs consisting of mild redness, erythema, and swelling around the injection site are anticipated. Grade 1 reactions should dissipate over several days to a week with no special treatment. All ISRs should be recorded on the Injection Site Reaction CRF page. Attempts to obtain photographs at the peak of severity and at follow-up visits which show resolution over time are encouraged. A ruler should be in the field of view to allow measurement of the size of the reaction. If the patient consents, the de-identified photograph(s) should be appended to the ECRF.

### **11.7 Pregnancy**

All female patients of childbearing potential will have a urine or serum pregnancy test performed at Screening, Baseline, and End of Treatment.

Female patients who become pregnant during the study should discontinue study medication immediately. The patient will receive counseling from the investigator or designee regarding the nature of the study medication and the potential risk on fetal development.

#### **11.7.1 Time Period for Collecting Pregnancy Information**

The time period for collecting information on whether a pregnancy occurs is from the Screening visit to four weeks after the last dose of study medication. Information on pregnancies identified prior to study product administration does not need to be reported to Heat Biologics.

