8. Women of childbearing potential or men of fathering potential must use adequate birth control measures (e.g., abstinence, oral contraceptives, intrauterine device, barrier method with spermicide, or surgical sterilization) during the study and for 6 months after receiving the last administration of study medication. Female patients of childbearing potential must test negative for pregnancy prior to enrolling in the trial.

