**6.1.1 Phase 1 Schedule of Events**

Procedure	Screening	Baseline	Week 1 	Weeks 2-6 	Week 7	Weeks 8-13 	Week 14	Week 17	Week 21	Week 25	Week 29 (EOT) 	Long-term Follow-up
Study Day	≤ -4 wks.	-3 to 1	1		43 (±1)		92 (±1)	113 (±3)	141 (±3)	169 (±3)	197 (±3)	Q3mos. 2 yrs; Q6mos. 3 rd yr
Baseline Documentation												
Informed Consent	X											
Verify All Eligibility Criteria	X											
Enrollment		X										
Medical History	X 	X										
Physical Exam 	X	X 			X		X				X	
Pathology Review	X											
12-lead ECG	X				X		X				X	
Laboratory Studies												
Immunologic Response 		X			X		X				X	
Hematology, Chemistry and LDH, Dipstick Urinalysis	X 	X 			X		X		X		X	
Pregnancy Test (urine or serum)	X 	X 									X	
Autoimmune Labs 		X					X				X	
Tumor Assessments												
Cystoscopy/Cytology for disease recurrence per SOC 					X				X			X 
Tumor collection for antigen screen			X									
Dosing												
Vesigenurtacel-L Administration 			X	X		X		X	X	X		
Other Clinical Assessments												
Autoimmune Phenomena 		X					X				X	
Adverse Events 			X	X	X	X	X	X	X	X	X	
Concomitant Medications	X 	X	X	X	X	X	X	X	X	X	X	
Survival and subsequent therapy												X

 Screening evaluations should be completed ≤2 weeks of first dose.

 PE, hematology, chemistry, LDH, dipstick urinalysis and pregnancy test do not need to be repeated at Baseline if they were performed at Screening within three days prior to first dose.

 First vesigenurtacel-L dose should occur 8-12 weeks (56-84 days) following TURBT or fulguration for patients with papillary disease and staging procedure for patients with CIS only regardless of the number of BCG instillations.

 Weekly study evaluations should be completed within ±1 day of the target visit date.

 EOT evaluations should be completed 4 weeks ±3 days after last dose of study vesigenurtacel-L or early discontinuation of study treatment.

 PE at screening and Week 29 (End of Treatment) will have a full examination of body systems and vital signs. Other PE evaluations will be limited to symptoms, weight and vital signs.

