## **6.2 Phase 2**

**6.2.1 Phase 2 Schedule of Events**

Procedure	Screen	Baseline	Week 1 	Weeks 2-6 	Week 7	Weeks 8-12 	Week 13	Weeks 14-16 	Week 25	Weeks 26-27 	Week 28	Week 37	Week 49	Weeks 50-52 	Week 56 (EOT) 	Long-term Follow-up
Study Day	≤ -4 wks.	-3 to 1	1		43 (±1)		85 (±1)		169 (±3)		190 (±3)	253 (±3)	337 (±3)		386 (±3)	Q3mos. 2yrs; Q6mos. 3 rd yr
Baseline Documentation																
Informed Consent	X															
Verify All Eligibility Criteria	X															
Enrollment/Randomization		X														
Medical History	X 	X														
Physical Exam 	X	X 					X								X	
Pathology Review	X															
12-lead ECG	X														X	
Laboratory Studies																
Immunologic Response 		X			X 		X				X 				X	
Hematology, Chemistry and LDH, Dipstick Urinalysis	X 	X 					X		X			X	X		X	
Pregnancy Test (urine or serum)	X 	X 													X	
Autoimmune Labs 		X													X	
Tumor Assessments																
Cystoscopy/Cytology for disease recurrence per SOC 							X		X			X	X			X 
Tumor collection for antigen screen			X													
Dosing																
Study Product Administration 			X	X	X	X		X		X	X			X		
BCG Administration 			X	X				X		X	X			X		
Other Clinical Assessments																
Autoimmune Phenomena 		X					X								X	
Adverse Events 			X	X	X	X	X	X	X	X	X	X	X	X	X	
Concomitant Medications	X 	X	X	X	X	X	X	X	X	X	X	X	X	X	X	
Survival and subsequent therapy																X

 Screening evaluations should be completed ≤ 2 weeks of first dose.

 PE, hematology, chemistry, LDH, dipstick urinalysis and pregnancy test do not need to be repeated at Baseline if they were performed at Screening within three days prior to first dose.

 First dose of study product should occur within 6 weeks of baseline staging procedure.

 Weekly study evaluations should be completed within ±1 day of the target visit date.

 EOT evaluations should be completed 4 weeks ±3 days after last dose of study product or early discontinuation of study treatment.

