-  PE at screening and Week 56 (End of Treatment) will have a full examination of body systems and vital signs. Other PE evaluations will be limited to symptoms, weight and vital signs.
-  70mL of heparinized blood, 10mL of non-heparinized blood, and 24mL urine will be collected at the indicated visits.
-  ANA, TSH, ESR, C-reactive protein are required. Other tests (e.g. RF, T3, T4, thyroid antibodies) will be performed only as clinically indicated.
-  All patients will have a cystoscopy/cytology performed at Week 13. If clinically indicated, a repeat biopsy will be performed. Patients with evidence of disease at an assessment may continue on treatment if judged by the investigator to be in the patient's best interest (e.g. would normally receive another course of BCG therapy as SOC). Upon discontinuation of study treatment, additional treatment will be at the discretion of the treating physician, and patients will continue in long-term follow-up on the study.
-  For Arms 1-4: Patients will receive study product as the number of intradermal injections required to reach the number of cells per dose with no more than 0.1 mL per injection (approximately 4-6 injections). Patients should remain on site for 30 minutes following each vaccination for observation of adverse events.
-  For Arms 1-3 only.
-  Includes eye exam for dry eyes, lymph node and joint assessment and skin exam for vitiligo and rashes.
-  AEs should be recorded from first dose through four weeks following the last dose of study medication regardless of the causal relationship to the study medication. AEs considered related to study medication should be recorded at any time regardless of when they occurred.
-  Samples to be collected prior to dosing
-  Cystoscopy/Cytology for disease recurrence per SOC (approximately every 3 months for 2 years then every 6 months for up to a year). Patients who are determined to have evidence of disease will have SOC treatment per the discretion of the investigator and will continue in long-term follow-up on the study.
-  Weekly study evaluations should be completed within  $\pm 3$  days of the target visit date.

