### 6.3 Long-term Follow-up Visits

All patients will be followed for the procedures listed below every 3 months from the date of the previous visit for 2 years then every 6 months from the date of the previous visit for a year or until study termination, whichever occurs first:

- Survival
- New anticancer treatments initiated after disease recurrence
- TURBT or fulguration procedures
- Cystectomy

In addition patients who have completed all study treatments or have discontinued study product dosing due to reason other than disease recurrence/progression will have the following procedures performed at each long-term follow-up visit:

- Cystoscopy/Cytology; biopsy if area suspicious for disease recurrence is identified at discretion of investigator (*Note: patients who have a biopsy performed will provide at least 4, non-stained, 10 micron sections for TCR sequencing and analysis of infiltrating T-cells.*) *If slides are not available, FFPE tissue (≥50 microns) is also acceptable.*

If a patient has recurrent/progressive disease and discontinues study treatment, the above disease assessment procedures will be discontinued, and subsequent long-term follow-up visits may be conducted via phone visit.

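### Female patients of childbearing potential must use contraception for six months after the last dose, but the protocol text requires no active pregnancy ascertainment after week four, about 22 of those 26 weeks

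*Protocol*

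**What the plan says.** **Contraception.** Protocol section 4.1, criterion 8: "Women of childbearing potential or men of fathering potential must use adequate birth control measures", and the period is "during the study and for 6 months after receiving the last administration of study medication". The synopsis and SAP section 3.3 repeat the criterion.

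**Collection period.** Protocol section 11.7.1 runs it "from the Screening visit to four weeks after the last dose of study medication".

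**Tests.** Section 11.7 states that female patients of childbearing potential "will have a urine or serum pregnancy test performed at Screening, Baseline, and End of Treatment". The Phase 2 schedule adds that "EOT evaluations should be completed 4 weeks ±3 days after last dose of study product"; the Phase 1 schedule says the same: "EOT evaluations should be completed 4 weeks ±3 days after last dose of study vesigenurtacel-L".

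**After EOT.** Section 6.3: "All patients will be followed for the procedures listed below every 3 months from the date of the previous visit". The list covers survival, later anticancer treatment, repeat resection or fulguration, and cystectomy. Cystoscopy and cytology are added for patients who completed treatment or stopped it for a reason other than recurrence or progression. Pregnancy is not listed, and neither schedule of events marks a pregnancy test in its follow-up column. Patients who stop study treatment are not lost to the trial: "patients will continue in long-term follow-up on the study".

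**What still operates later.** Under section 11.7.2 the investigator notifies the sponsor within one week of learning of a patient's pregnancy, and reports an SAE from a post-study pregnancy if it is considered reasonably related to the product. Sections 11.8 and 11.8.5 have related AEs recorded however late they occur.

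**The concern.** The protocol treats the six months after dosing as a time when conception should be avoided, yet it stops looking for conceptions after the first four weeks. No patient had received this product before the trial (section 1.4), and section 11.7 provides for counselling about possible fetal risk. A pregnancy conceived in months 2 to 6 is therefore an event that the protocol tries to prevent, but nothing in its text prompts the site to ask about it.

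What is at stake is completeness of safety information on a small number of pregnancies and their outcomes. The SAP's safety section lists no pregnancy variable, so no planned analysis depends on it.

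**Working it through.** **Inputs**
- Contraception after the last dose: 6 months, taken as 26 weeks = 182 days (section 4.1, criterion 8).
- End of collection: day 28 after the last dose (section 11.7.1).
- Last scheduled test: EOT, day 28 ± 3 after the last dose (schedules of events, footnote 5).
- Follow-up contacts: every 3 months from the previous visit (section 6.3), taken as 91 days.

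**Reproducing the plan's visit days.** EOT = last dose day + 28.
- Phase 1: 169 + 28 = 197; the protocol states Day 197.
- Phase 2: 358 + 28 = 386; the protocol states Day 386.

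So the last test and the end of collection coincide.

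**Length without required ascertainment**
- 182 − 28 = 154 days; 154 / 7 = 22 weeks; 154 / 182 = 85%.
- With 6 months as 180 to 184 days: (180 − 28) / 7 = 21.7 weeks to (184 − 28) / 7 = 22.3 weeks.
- With 6 months as 182.6 days and the last test at day 31 or day 25: 21.7 to 22.5 weeks.

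The count starts at each patient's own last dose, so it does not depend on how many doses she received.

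**Where existing contacts fall**
- First: 28 + 91 = day 119 (week 17).
- Second: 119 + 91 = day 210 (week 30). With EOT ± 3 days it falls on days 207 to 213, always after day 182.

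**Time left unasked if a question is added**
- First contact only: 182 − 119 = 63 days, and 63 / 154 = 41%.
- Both contacts: 0 days.

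**Time asked about is not the same as conceptions found.** Assume that a pregnancy is recognised k weeks after conception. The documents give no value for k; 4 to 8 is my assumption. A conception after (contact day − 7k) is not yet recognised at that contact. The unrecognised part of the 154 days is:

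| k (weeks) | First contact only: 182 − (119 − 7k) | Both contacts: 182 − (210 − 7k) |
|---|---|---|
| 4 | 91 days (59%) | 0 days |
| 6 | 105 days (68%) | 14 days (9%) |
| 8 | 119 days (77%) | 28 days (18%) |

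One contact is not enough. Two cover the whole period by question and most of it by recognition.

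**The case against.** **The window is a choice.** Four weeks matches the general AE window in section 11.8.5, and nothing in the documents says that the collection period must equal the contraception period. One rule prevents exposure; the other limits active collection. This stands: a reader might infer that the two sections contradict each other, and they do not. The AE window still does not explain why asking should stop about five months before the precaution does.

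**Later pregnancies can still be reported.** This also stands. A reader might infer that a pregnancy after week 4 has no reporting route, or surfaces only if the patient volunteers it. The documents do not support that. Sections 11.7.2, 11.8 and 11.8.5 keep passive routes open, and many patients attend 3-monthly cystoscopy visits where a pregnancy may come to light. Section 11.7.2 also says that investigators need not actively seek SAEs from post-study pregnancies in former participants, but that does not settle the rule for patients still in follow-up. These routes all depend on the pregnancy becoming known; none prompts the question.

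**The 26 weeks rest on a reading.** Criterion 8 covers the study as well as the six months. If long-term follow-up counts as part of the study, contraception could run longer than 26 weeks. The figure of 22 of 26 applies to the six-month clause alone.

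**Unseen material.** The study procedures manual and the consent form were not available and may ask about pregnancy. The finding concerns the protocol text only.

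**Conclusion.** The concern holds as a minor safety-collection point. For female patients of childbearing potential, the protocol text requires no active ascertainment for about 22 of the 26 weeks of post-dose contraception (154 of 182 days, 85%; 21.7 to 22.5 weeks across month lengths and visit windows).

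Limits:
- The 85% is a share of time. A reader might take it as a share of pregnancies missed; the documents give no number of women of childbearing potential, so no count can be derived. I assume few pregnancies.
- A reader might extend the gap to partners of male patients. Section 11.7.3 provides for attempted collection of partner pregnancies arising during study participation, with no stated end point, and this may already reach into follow-up. No gap is claimed there.
- Efficacy analyses and planned safety comparisons are unaffected.

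**What to change.** 1. In section 11.7.1, change the end of collection from four weeks to six months after the last dose.
2. Add one pregnancy question at the first two existing 3-monthly follow-up contacts after EOT, about weeks 17 and 30 after the last dose. A telephone question is enough; section 6.3 already allows phone visits for patients with recurrent or progressive disease who have stopped treatment.
3. In Phase 1, apply this only to patients still within that period. There may be few or none, because Phase 2 dosing could start only after all 10 Phase 1 patients had been dosed, and SAP section 3.4 already refers to randomisation in the past tense.

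Section 11.7.3 need not change for this purpose. Stating an end point there would be a clarification, and it should not shorten present coverage.

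**Cost.** A short protocol amendment with IRB/IEC review, a line in the schedule of events, one data field and slight extra site reporting. No new visit, test or staff. Some conceptions close to month 6 may still be unrecognised at week 30.
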